### 17.2. Safety monitoring and stopping rules

In order to monitor the safety of the treatment in small cohorts of patients, the Bayesian approach of Thall, et al. [33], as extended by Thall and Sung [34], for monitoring toxicity will be used. We have planned the monitoring of toxicity to ensure that the proportion of patients with non-hematological toxicity defined as any non-hematological toxicity of grade 3 or higher after 3 and 6 cycles of induction was not higher than an acceptable level of 25%. The prior probability of toxicity (25%) is modeled by a beta distribution [Beta (0.5,1.5)]. We will stop the enrolment in the experimental cohort if the posterior probability of the treatment being more toxic than expected is greater than 90%. Patients will be monitored, without suspending the enrollment, according to the following stopping boundaries for toxicity in cohorts of five patients as per assessment every 3 cycles:

Patients Enrolled	Stop the enrollment in the cohort if the relevant toxicities are greater or equal to:
5	3
10	5
15	7
20	9
25	10
30	12
35	13
40	15

Demographics and patients' characteristics will be summarized by descriptive statistics. Point estimates of efficacy and toxicity will be provided with 95% confidence intervals. Overall response rate will be calculated as the sum of complete and partial response rates. Time-to event endpoints (progression free survival, overall survival) will be estimated by the Kaplan-Meier method. For the safety analyses, frequency of toxicities will be reported by type and grade according to the National Cancer Institute Common Terminology Criteria for Adverse Events (version 5.0).

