**Safety monitoring and stopping rules:**

In order to monitor the safety of the treatment in small cohorts of patients, the Bayesian approach of Thall, et al (1995) as extended by Thall and Sung (1998), for monitoring toxicity will be used. We have planned the monitoring of toxicity to ensure that the proportion of patients with non-hematological toxicity (defined as any non-hematological toxicity of grade 3 or higher or treatment interruption for safety reasons or any toxic death) after 3 and 6 cycles of induction is not higher than an acceptable level of 25%. The prior probability of toxicity (25%) is modeled by a beta distribution [Beta (0.5,1.5)]. We will stop the enrolment in the experimental cohort if the posterior probability of the treatment being more toxic than expected is greater than 90%. Patients will be monitored, without suspending the enrollment, according to the following stopping boundaries for toxicity in cohorts of five patients as per assessment every 3 cycles:

[figure not shown]
Patients assessed for toxicity	Stop the enrollment in the cohort if the relevant toxicities are greater or equal to:
5	3
10	5
15	7
20	9
25	10
30	12
35	13
40	15

Demographics and patients' characteristics will be summarized by descriptive statistics. Point estimates of efficacy and toxicity will be provided with 95% confidence intervals. Overall response rate will be calculated as the sum of complete and partial response rates. Time-to-event endpoints (progression free survival, overall survival) will be estimated by the Kaplan-Meier method. For the safety analyses, both at patient level and at therapy cycle level, summaries of incidence rates (frequency and percentages) of individual adverse events will be reported by type and grade according to the National Cancer Institute Common Terminology Criteria for Adverse Events (version 5.0).

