### **9.4. Secondary Endpoint**

- **Overall survival (OS) rate**, measured from the date of starting therapy to the date of death from any cause. Patients alive and patients who are lost to follow up at the time of the final

analysis will be censored at the date of the last contact. The minimum follow-up time required for OS assessment for all patients will be 2 years.

- **Progression-free survival (PFS) rate**, measured from the date of starting therapy to the date of disease progression, relapse or death from any cause. Responding patients and patients who are lost to follow up will be censored at their last assessment date. Patients who will have no tumor assessment after the start of therapy due to interruption of both drugs will be considered failures at the date of treatment interruption in the PFS analysis. The minimum follow-up time required for PFS assessment for all patients will be 2 years.
- **Treatment safety** through the measurement of: patients' withdrawal rate, incidence, type and grade of any adverse event (AE) and serious adverse event (SAE), hospitalization rate throughout the study, and patients' compliance to oral treatment.

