Patients who will interrupt therapy (for any reason), if at least in stable disease at time of treatment discontinuation, will enter the follow-up period and will be re-evaluated for response every 6 months for 2 years or until progression/start of new anti-lymphoma therapy/death. If these patients experience progression/start of new lymphoma treatment will be followed up for survival for a total of 2 years from treatment discontinuation. These patients are however considered evaluable for PFS and OS.

Non-responder, relapsing or progressive patients will be treated according to best clinical practice.

These patients are however considered evaluable for OS.

CT scans have to be performed at baseline, after induction cycle 3 and 6 (EOI), every 3 months during the first year of maintenance, every 4 months during the second year of maintenance, at the end of treatment after 2 years of maintenance or in case of early withdrawal (EOT), at relapse/progression and during follow-up.

PET scans are mandatory at baseline, after induction cycle 3 and 6 (EOI), at the end of treatment after 2 years of maintenance or in case of early withdrawal (EOT) and at relapse/progression. At all additional timepoints (including follow-up) they are optional and will be done at clinician discretion only if in accordance with center clinical practice.

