### **Obinutuzumab**

There will be no obinutuzumab dose modification in this study. Consider treatment interruption if patients experience an infection, Grade 3 or 4 cytopenia, or a  $\geq$  Grade 2 non-hematologic toxicity. Any NCI CTCAE (v. 5.0) toxicity Grade  $\geq 3$  in severity that is deemed related to obinutuzumab treatment will require interruption of study treatment until resolution to Grade  $\leq 2$  or  $\geq 80\%$  of baseline, whichever is lower.

Resumption of obinutuzumab treatment may be considered in patients with resolution of toxicities to Grade  $\leq 1$  within 2 weeks at the discretion of the investigator, after consultation with the Medical Monitor. Failure of such toxicities to resolve after 2-week delay in study treatment will require permanent discontinuation of obinutuzumab.

Continuation of study treatment following dose delays beyond 2 weeks will require consultation with and approval of the Medical Monitor based on an assessment of the benefit-risk analysis of continuing to delay study treatment.

Patients in whom toxicities have not resolved (i.e., to Grade  $\leq 1$  or  $\geq 80\%$  of baseline) may have their study treatment delayed by up to 2 weeks. If all study drug-related toxicities have resolved to Grade  $\leq 1$  or  $\geq 80\%$  of baseline, the patient may resume idelalisib and obinutuzumab dosing on the regular every-28-day schedule.

Patients who do not fulfill the criteria for dosing after the additional 2 weeks have elapsed may be discontinued from study treatment and be followed for safety outcomes. Exceptions on the basis of ongoing clinical benefit may be allowed following a careful assessment and discussion of risk versus benefit with the patient by the investigator and approval from the Medical Monitor. In addition, delay of therapy because of toxicities not attributed to study drug may not require discontinuation and will be discussed with the Medical Monitor.

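### The toxicity stopping rule has one set of boundaries but two event definitions, so the Synopsis can say stop where Section 17.2 says continue

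*Combined protocol and SAP*

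**What the plan says.** The rule appears in the Synopsis (safety monitoring and stopping rules) and in Section 17.2. Both are current text. They share the 25% acceptable level, the Beta(0.5, 1.5) prior, the 90% posterior cut-off, monitoring without suspending enrolment, and the boundaries 3/5, 5/10, 7/15, 9/20, 10/25, 12/30, 13/35 and 15/40.

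They differ in two respects:

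| | Synopsis | Section 17.2 |
|---|---|---|
| Event | "any non-hematological toxicity of grade 3 or higher or treatment interruption for safety reasons or any toxic death" | "defined as any non-hematological toxicity of grade 3 or higher after 3 and 6 cycles of induction" |
| First column of the table | "Patients assessed for toxicity" | "Patients Enrolled" |

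Both place the looks "in cohorts of five patients as per assessment every 3 cycles". Neither defines treatment interruption, and other sections use the term in different senses:

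- **Section 9.4 (PFS):** patients who interrupt both drugs and have no tumor assessment are "considered failures at the date of treatment interruption in the PFS analysis". Here it means the end of treatment.
- **Section 10.1:** the follow-up rule for "Patients who will interrupt therapy (for any reason), if at least in stable disease at time of treatment discontinuation" again treats it as the end of treatment.
- **Section 13.12 (Obinutuzumab):** "Consider treatment interruption if patients experience an infection, Grade 3 or 4 cytopenia" describes a temporary hold.
- **Section 17.3:** adverse events leading to interruption and those leading to discontinuation are listed separately.

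**The concern.** A stopping boundary has meaning only for the event it counts. Here the same eight numbers are attached to two events, one contained in the other, and nothing ranks the two texts. The Synopsis cannot be read as an abbreviation of Section 17.2, because it adds two components that the body lacks.

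The extra component that matters is interruption. A non-hematological toxic death is already grade 5 and counts under either text, so the toxic-death clause adds only deaths from hematological toxicity. Interruption without a grade 3 or higher non-hematological event is reachable under Section 13.12. CMV viremia or active CMV infection of any grade leads to an idelalisib hold, and confirmed PJP of any grade leads to permanent idelalisib discontinuation. Below grade 3, neither counts in Section 17.2. If stopping one drug is enough, the PJP case keeps the gap open even when interruption means permanent stopping.

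It is also unclear whether one drug or both must be interrupted. Nor is it clear whether an interruption for cytopenia alone counts, since the quantity being defined is called non-hematological toxicity.

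At stake is whether accrual continues at a look, under the only pre-specified toxicity boundary in the trial.

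**Working it through.** **Inputs.** The limit, prior, cut-off and boundaries come from the Synopsis and Section 17.2. The documents give neither a rate for this event nor the share of patients who would have only the extra components, so both are assumed below.

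**1. The plan's own boundaries.** After x events in n patients the posterior is Beta(0.5 + x, 1.5 + n − x), and the rule stops when P(p > 0.25) exceeds 0.90. The smallest such x at n = 5, 10, …, 40 is 3, 5, 7, 8, 10, 11, 13, 14. Five of the eight printed values agree. At n = 20, 30 and 40 the print is one event higher, although 8/20 (0.913), 11/30 (0.908) and 14/40 (0.909) already exceed 0.90. All eight printed values are reproduced if the standard rate is itself given a Beta(25, 75) prior, which the documents do not state. This mismatch is a separate point. Everything below uses the printed table. None of these inputs depends on how the event is defined.

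**2. One data set, two decisions.** Five patients are assessed. Two have a grade 3 or higher non-hematological event. One has only a safety interruption, for instance an idelalisib stop for PJP below grade 3.

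- Synopsis: x = 3, Beta(3.5, 3.5), P(p > 0.25) = 0.915, boundary 3 reached: stop.
- Section 17.2: x = 2, Beta(2.5, 4.5), P(p > 0.25) = 0.702, boundary not reached: continue.

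**3. How often the texts would disagree.** Exact binomial recursion over the eight looks gives the probability of ever crossing a printed boundary:

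| True event rate | 25% | 27% | 30% | 33% | 35% | 38% | 40% |
|---|---|---|---|---|---|---|---|
| P(cross) | 0.208 | 0.276 | 0.397 | 0.531 | 0.621 | 0.743 | 0.811 |

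Every Section 17.2 event is also a Synopsis event. With the same denominator, Section 17.2 therefore never stops unless the Synopsis does, and the probability of disagreement is the difference between the two crossing probabilities:

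| Assumed Synopsis rate | Gap 2 points | Gap 5 points | Gap 10 points |
|---|---|---|---|
| 40% | 0.811 − 0.743 = 0.068 | 0.811 − 0.621 = 0.190 | 0.811 − 0.397 = 0.414 |
| 35% | 0.621 − 0.531 ≈ 0.09 | 0.621 − 0.397 ≈ 0.22 | 0.621 − 0.208 ≈ 0.41 |

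Seen from the other side, if the grade 3 or higher rate sits exactly at the 25% limit, Section 17.2 stops with probability 0.21. The Synopsis stops with 0.28, 0.40 or 0.62 for gaps of 2, 5 or 10 points.

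**4. The header (secondary, literal reading only).** Accrual is not suspended for toxicity looks, so enrolled patients can outnumber assessed ones. Read literally, the Section 17.2 header treats the unassessed as event-free. Take a 40% true rate and one patient every 12.7 days (43 patients in 18 months):

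- **By assessed patients**, the looks at 5 to 35 (those before accrual ends) stop with exact probability 0.787.
- **By enrolled patients, each row checked once at the nth enrolment**, simulation gives 0.38 if events become known only at day 84, 0.60 if they are uniform over 84 days, and 0.72 if uniform over the first 28 days. One recheck of the 7/15 row when all 15 are assessed gives about 0.5, 0.63 and 0.73.
- **By enrolled patients, the latest row rechecked continuously**, which neither text describes, the range is 0.66 to 0.81: about 0.13 below to 0.02 above the assessed figure.

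**5. Events in cycles 4–6.** Both texts monitor after 3 and after 6 cycles. At 12.7 days per patient the fifth patient starts on day 51 and completes cycle 6 on day 51 + 168 = 219. By then 11 patients have passed day 84, so row 10 has been reached before row 5 is final. Neither text says how a later event changes a row already passed.

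**The case against.** The strongest reply is about size. The disagreement probabilities restate an assumed gap: they illustrate the effect and do not measure it. If interruption means permanently ending both drugs, few patients may fall between the two definitions. That is correct, and the documents cannot settle it, because they do not define the term.

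Second, the Section 17.2 prose ties the looks to assessment every 3 cycles, which points to assessed patients despite the header. That also stands. The header figures hold only for a literal reading, and they depend on assumed event timing and on a constant accrual rate that ignores the stage 1 pause at 15 patients, apart from the recheck variants. Nor does the header work in one direction only: three early events among the first five enrolled would reach the Section 17.2 boundary before five patients are assessed.

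Third, under Section 18 the DSMB reviews all available safety data about every 3 months and may recommend ending recruitment on grounds outside the table. This softens the consequence, but it does not say which event the table counts.

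Fourth, the treatment of cycle 4–6 events is an omission common to both texts, not a conflict between them. It is raised because the same sentence has to be rewritten; the main point does not rest on it.

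**Conclusion.** The concern holds and must be fixed. The protocol contains two stopping rules with identical numbers, and the same patients can yield opposite decisions as early as the first look. From the event definition alone, the conflict always runs one way: the Synopsis stops and Section 17.2 continues. At an assumed Synopsis-event rate of 35% to 40%, disagreement runs from about 0.07 to 0.41 for assumed gaps of 2 to 10 points. It approaches zero as the gap does. These figures use the printed boundaries and independent patients with a constant event rate. The header difference is a real but lesser inconsistency.

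**What to change.** 1. Adopt one event definition and print it word for word in the Synopsis and Section 17.2. The choice of event is the sponsor's.
2. If interruption stays in the definition, state whether it means a temporary hold or permanent discontinuation, whether of either drug or both, and whether an interruption for hematological toxicity alone counts.
3. State that the 25% limit, the prior and the boundaries refer to that event. When the table is reissued, also resolve the one-event mismatch at n = 20, 30 and 40, or state the comparator prior.
4. Head both tables with patients assessed for toxicity. State that the look at n takes place when the first n treated patients have each completed the cycle 3 assessment or had an event.
5. State how events in cycles 4–6 update the count.

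The cost is protocol and SAP wording only, with no extra patients or data.

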Study design	
Single arm, prospective, multi-centric, phase II study.
 
Patients with histologically confirmed follicular lymphoma, in need of a systemic approach and failing (i.e. with refractory disease [no response or response lasting less than 6 months at any previous line of treatment] or with a proven disease relapse) at least 2 previous lines of treatment, including any antibody directed against the CD20 antigen-containing chemotherapy, will undergo a combined chemo-free treatment with obinutuzumab and idelalisib.
 
Obinutuzumab will be administered intravenously at a flat dose of 1000 mg on day 1, 8, 15 of the first cycle, then repeated on day 1 of each subsequent cycle, for 6 cycles (each cycle is completed in 28 days). Idelalisib will be given concomitantly with obinutuzumab and on a daily 150 mg bid schedule. For patients achieving at least a partial response at the end of induction, a maintenance phase with obinutuzumab is scheduled (on day 1 every two months for two years or until progression or unacceptable toxicity, whichever comes first)

	
If one of the two drugs has to be permanently discontinued due to any cause, patient may continue treatment with the other agent if it is judged to be a clinical benefit. Patients with at least a stable disease will enter the follow-up phase and will be followed with repeated CT scans every six months for two years or until death/progression occurs (whichever comes first).
 
Patients with progressive disease, whenever progression is documented, will enter a survival follow up period of two years after PD was documented. These patients are however considered evaluable for OS.

Duration of the study	1.5 year of enrolment + 6 months of induction + 2 years of maintenance+ 2 years of (survival) follow up (ca. 6,5 years in total)
Number of patients	43 patients (stage I: 15 patients; stage II: 28 patients)

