## 10.3. Duration of the study

Patients will be recruited over 1.5 year + 6 months of induction + 2 years of maintenance and followed for 2 years after the end of the treatment phase (6,5 years).

End of study is defined by the last visit planned by the protocol of the last patient in follow-up that means 2 years after the EOT visit (LPLV). The Final Study Report will be provided after the end of the Study.

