## 13.3. Treatment schedule and design

All eligible patients will undergo a combined treatment with obinutuzumab and idelalisib for 6 cycles (each cycle is completed in 28 days).

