## 18. INDEPENDENT DATA SAFETY MONITORING BOARD (DSMB)

The FIL on its own initiative and responsibility set up an independent external DSMB. The DSMB consist in Experts independent from the sponsor.

The aim of the DSMB is to assess, at intervals (every 3 cycles) during the course of the trial, the progress of the trial, the trial safety data and the trial outcome data with a view to recommending whether the trial should continue, be modified or be terminated.

The DSMB will be composed by:

- Three independent clinicians with expertise in the treatment of FL
- The biostatistician of the study
- An independent statistician with expertise in the methodology of clinical trials and data analysis.

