### Timing of Analyses

#### *Interim Analyses*

The DSMB will have access to serious adverse events requiring expedited reporting and will be provided with accumulating safety data on a regular basis. An interim safety review will be conducted by the DSMB at ~3 months after the first subject is enrolled. Thereafter, interim safety reviews will be performed by the DSMB at intervals of ~3 months, according to the availability of the safety monitoring results; the specific frequency of these reviews will depend upon the rate at which the trial is enrolled, the nature of any emerging safety signals, and monitoring recommendations from the DSMB. At each review, all available safety data will be summarized and evaluated. The analyses will offer opportunities to assess early for evidence of substantial clinical benefit.

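### As most naturally read, the toxicity boundaries act only at each cohort's 3-cycle assessment while enrolment continues; one sentence letting them act once the count is reached would spare about one to three patients in a trial that stops

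*Combined protocol and SAP*

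**What the plan says.** Section 17.2 of the protocol gives a Bayesian rule for non-hematological toxicity with a table of limits: 3 of 5 patients, 5 of 10, 7 of 15, 9 of 20, 10 of 25, 12 of 30, 13 of 35 and 15 of 40. The limits are applied "according to the following stopping boundaries for toxicity in cohorts of five patients as per assessment every 3 cycles". The same sentence begins "Patients will be monitored, without suspending the enrollment". The synopsis repeats the rule. Toxicity is judged after 3 and after 6 induction cycles.

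The two tables differ in the heading of the first column. Section 17.2 counts patients enrolled; the synopsis counts patients assessed for toxicity. Neither place says whether a limit acts when its count is reached or only when the cohort is assessed.

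Section 18 has the DSMB look at the trial "at intervals (every 3 cycles) during the course of the trial". Under Interim Analyses it adds: "An interim safety review will be conducted by the DSMB at ~3 months after the first subject is enrolled". Later reviews follow about every 3 months. The board also has access to serious adverse events that require expedited reporting, and it may recommend ending recruitment. Section 18 does not mention the table of limits.

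**The concern.** The rule is there to protect patients in small cohorts. A patient who has had a qualifying toxicity stays counted, so the number of such patients among the first five can only rise. Once it reaches 3, the first limit will be met whatever happens to the other two. Waiting until the fifth patient has completed 3 cycles adds no information to that decision, yet new patients keep starting a regimen that the trial's own rule already classes as too toxic. At the planned accrual, most of Stage 1 (15 patients) could be on treatment before the first limit acts.

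**Working it through.** **Inputs from the documents.** 43 patients, 15 of them in Stage 1 (synopsis); "Patients will be recruited over 1.5 year + 6 months of induction" (section 10.3; the synopsis agrees); cycles of 28 days (section 13.3); the printed limits (section 17.2); accrual suspended at 15 patients for the response analysis (section 17.1).

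**Assumptions not in the documents.** Constant accrual at the planned average; onset of toxicity uniform over the 84 days of 3 cycles unless stated; a month of 30.44 days.

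**The plan's own limits.** With the stated Beta(0.5, 1.5) prior, 3 toxic patients of 5 give a Beta(3.5, 3.5) posterior, and P(rate > 0.25) = 0.915, above 0.90. Two of 5 give Beta(2.5, 4.5) and 0.702. The first row is therefore reproduced. Against a fixed 25%, the rows for 10, 15, 25 and 35 are reproduced too, while those for 20, 30 and 40 come out one lower (8, 11, 14). The timing argument uses the printed values throughout.

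**Patients started at the first reading.**
- Accrual: 43 / 18 = 2.39 per month. Three cycles: 84 / 30.44 = 2.76 months.
- Started when the fifth patient completes 3 cycles: 5 + 2.39 × 2.76 = 11.6. With random (Poisson) arrivals the mean is 11.5, with a 5th to 95th percentile range of 8 to 15.
- Accrual over 24 months: 43 / 24 = 1.79 per month, and 5 + 1.79 × 2.76 = 9.9.
- If the 18 months include a Stage 1 pause of 3 to 6 cycles, accrual outside the pause is faster and the figure is 12.8 to 14.9.

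**How often the first limit is crossed.** P(at least 3 of 5) is 10% at a true rate of 25%, 32% at 40% and 50% at 50%.

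**How often that crossing is fixed early.** This needs no assumption about onset. Given at least 3 of 5, the chance that the first four patients already include 3 is P(at least 3 of 4) / P(at least 3 of 5): 49% at 25%, 56% at 40% and 63% at 50%. With even accrual the fourth patient starts 30.44 / 2.39 = 12.7 days before the fifth, so in these cases the stop is fixed at least 12.7 days before the reading. With uniform onset, the crossing is fixed more than 14 days early in 91 to 93% of cases.

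**Whole trial.** Simulation of 6,000 trials per scenario, with Poisson accrual, the pause at 15, the printed limits, no reporting delay and each patient counted once:

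| True rate | P(stop), both rules | Treated at stop: scheduled reading | Treated at stop: at crossing | Difference |
|---|---|---|---|---|
| 40% | 0.816 | 20.5 | 17.7 | 2.8 |
| 50% | 0.982 | 16.7 | 13.8 | 2.9 |
| 60% | 1.000 | 13.5 | 10.3 | 3.2 |

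The stop comes 1.5 to 1.6 months earlier. At the acceptable 25% rate P(stop) is 0.21 under both rules. With late onset the saving is 2.0 to 2.3 patients, and with early onset 3.7 to 4.2.

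**Reporting delay.** If each event reaches the count late, and the scheduled reading remains as the latest time to act, the saving over true rates of 40 to 60% is about 2 patients at 14 days and 1.2 to 1.5 at 28 days.

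**The case against.** **The text does not say outright that the rule waits.** This stands in part. The heading in section 17.2 counts enrolled patients, and the reference to every 3 cycles could mean the recurring DSMB review. On that reading the first look comes at about 3 months, when about 2.39 × 3 = 7 patients have started. The words about assessment and the synopsis heading favour the waiting reading, but do not settle it.

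**The trial has other safeguards.** A reader might infer that nothing can stop enrolment before 11 or 12 patients have started. The documents do not support that. The DSMB sees expedited serious events, evaluates all available safety data, can review more often if signals emerge, and may recommend ending recruitment. The sponsor may also stop the trial (section 14.5). Three toxic patients of five would hardly go unseen. These powers are discretionary, however, and none is tied to the table.

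**The saving depends on reporting.** This stands. Serious events and events of special interest are due within 24 hours (section 16.3). Non-serious grade 3 events also qualify, and they reach the CRF as soon as possible, at the latest before each monitoring visit (section 20.2). If the scheduled reading were not kept as a latest time, the saving at a 28-day delay would be smaller still, about 0.6 to 1.3 patients.

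**Counting events is not the same as counting patients.** This stands, and it shapes the fix. The plan monitors a proportion of patients. A running count of events would be a different rule: with Poisson events per patient (an assumption), P(stop) at the acceptable 25% rate rises from 0.21 to 0.40.

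**Conclusion.** The point holds as a gap in the wording with a modest, one-sided effect on patient exposure. As most naturally read, the limits act only at the 3-cycle assessment of each cohort of five, by which time about 11 to 12 patients have started at the planned accrual (about 10 with slower accrual).

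A reader might infer that trials will often reach a stop and then wait. The supported statement is conditional: when a limit is going to be crossed, the crossing is usually fixed before the reading. The first limit itself is crossed in only about 10% of trials at 25% true toxicity, and in 50% at 50%.

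A trial that stops treats about 3 fewer patients with immediate reporting, and about 1 to 2 fewer with realistic delays. These figures rest on even average accrual, true toxicity of 40 to 60% and onset uniform over 84 days. They were worked out for the 3-cycle window only. That the probability of stopping does not change holds for any fixed window, because the same patients are counted against the same limits. Since the change makes a stop no more likely, it is worth making.

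**What to change.** In section 17.2 and the synopsis, use the same heading for the first column of the table and add:

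> A boundary is met as soon as the number of patients with at least one qualifying toxicity (each patient counted once, within the 3- or 6-cycle assessment window already defined) among the first 5, 10, ..., 40 treated patients reaches the tabulated value. Enrolment then stops without waiting for the remaining patients of that cohort to complete the assessment. The 3- and 6-cycle assessments confirm patients without events.

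The two sections must also agree on what qualifies. The synopsis adds treatment interruption for safety reasons and toxic death to grade 3 or higher non-hematological toxicity; section 17.2 does not.

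The cost is a running per-patient count and, for the full gain, prompt entry of non-serious grade 3 or higher events. No extra patients or visits are needed. The limits do not change and, for a given window, neither does the probability of stopping.

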## **17. STATISTICAL CONSIDERATIONS**

### **17.1. Sample size**

Optimal Simon's two-stage design [32] has been used to calculate the sample size.

The null hypothesis that the true response rate is 55% (response rate of idelalisib single agent) [6] will be tested against a one-sided alternative response rate of 75% (response of obinutuzumab in combination) [23]. Last available clinical response will be considered for patients who will permanently discontinue for any cause both drugs of the experimental combination before the completion of the 6th cycle (planned duration of induction phase).

For the first stage, the accrual will be suspended when 15 patients will have started experimental therapy. If there are 9 or fewer responses in these 15 patients, the study will be stopped.

Otherwise, enrollment will be reopened until 28 additional patients will start experimental therapy for a total of 43. The null hypothesis will be rejected if 29 or more responses are observed in 43 patients.

This design yields a type I error rate of 5% and power of 80% when the true response rate is 75%.

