### 17.3. Statistical analysis plan

#### Analysis population

Both efficacy and safety analyses will be conducted on all patients receiving at least one dose of planned therapy.

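### Does the unspecified 95% interval for response rate conflict with the one-sided 5% two-stage rule of 29 or more responses in 43?

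*Combined protocol and SAP*

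**What the plan says.** Section 17.1 (Sample size) sets out the primary test. "Optimal Simon's two-stage design [32] has been used to calculate the sample size". The null rate is 55%, and it "will be tested against a one-sided alternative response rate of 75"%. The interim rule is: "If there are 9 or fewer responses in these 15 patients, the study will be stopped". The final rule is: "The null hypothesis will be rejected if 29 or more responses are observed in 43 patients". The stated operating characteristics are a 5% type I error and 80% power at 75%. The synopsis repeats all of this.

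Estimation is covered in the closing paragraph of section 17.2 and again in the synopsis: "Point estimates of efficacy and toxicity will be provided with 95% confidence intervals", and "Overall response rate will be calculated as the sum of complete and partial response rates". Section 17.3 adds the analysis population ("Both efficacy and safety analyses will be conducted on all patients receiving at least one dose of planned therapy") and the adverse-event summaries.

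Neither document section names an interval method, says whether the interval is one- or two-sided, names a p-value method, or says how the interval relates to the count rule. No p-value for response rate is promised anywhere.

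**The concern.** A reader expects a test and an interval for the same parameter to agree. Here the test spends 5% in one tail, while a 95% interval, read in the usual two-sided way, spends 2.5% there. The test also takes credit for the stage 1 stop, which an ordinary binomial interval ignores. At or just above the threshold, a report could therefore state that 55% was rejected beside an interval that includes 55%. If someone added an ordinary exact p-value, it could exceed 0.05. Because the method is not named, at 30 responses the choice of method would settle whether 55% lies inside the interval, and that choice could be made after the data are seen. At stake would be the clarity of the headline result in a borderline trial.

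**Working it through.** **Inputs** (section 17.1): n1 = 15, stop at 9 or fewer; n2 = 28, N = 43; reject at 29 or more; p0 = 0.55, p1 = 0.75, one-sided. I assume exactly 43 treated patients.

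**1. The plan's own figures.** The probability of rejecting is

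R(p) = Σ over x = 10 to 15 of P[Bin(15, p) = x] × P[Bin(28, p) ≥ 29 − x].

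At p = 0.55 the six terms are 0.14036 × 0.11872, 0.07798 × 0.21350, 0.03177 × 0.34038, 0.00896 × 0.48746, 0.00156 × 0.63556 and 0.00013 × 0.76539. They sum to 0.0496. At p = 0.75 the same sum gives 0.805. The stated 5% and 80% are reproduced.

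**2. Two-sided 95% intervals against the rule.**

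| Responses | Rate | Rule | Exact | Wilson | Jeffreys | Wald |
|---|---|---|---|---|---|---|
| 29/43 | 67.4% | reject | 51.5–80.9% | 52.5–79.5% | 52.7–80.0% | 53.4–81.4% |
| 30/43 | 69.8% | reject | 53.9–82.8% | 54.9–81.4% | 55.1–81.9% | 56.0–83.5% |
| 31/43 | 72.1% | reject | 56.3–84.7% | 57.3–83.3% | 57.6–83.8% | 58.7–85.5% |

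All four contain 55% at 29. Exact and Wilson contain it at 30. None does at 31.

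**3. Is the two-stage design the cause?** Write T(k, p) for the probability of passing stage 1 and reaching at least k responses in 43. Solving T(k, p) = 0.025 for p gives the lower limit of a two-stage 95% interval: 0.525 at 29 and 0.546 at 30. Both are below 0.55, so an interval that respects the design still contains 55% at these counts. Solving T(k, p) = 0.05 gives 0.531 at 28, 0.5503 at 29 and 0.571 at 30, which agrees with the rule on both sides of the threshold. At the 95% level, the difference in level is therefore enough to produce the mismatch.

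**4. The p-value.** The single-stage value P[Bin(43, 0.55) ≥ 29] is 0.067. The value that follows the design is T(29, 0.55) = 0.0496, the same quantity as the type I error in step 1. The difference, 0.0672 − 0.0496 = 0.0176, is the null probability of reaching 29 in 43 after 9 or fewer in the first 15. Under the rule such trials stop at 15 and never reach 43.

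**5. How often it could arise.**

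| True rate | P(exactly 29) | P(29 or 30) | P(reject) | Exactly 29, share of rejections | 29 or 30, share of rejections |
|---|---|---|---|---|---|
| 75% | 0.046 | 0.119 | 0.805 | 5.8% | 14.8% |
| 70% | 0.080 | 0.179 | 0.592 | 13.6% | 30.3% |

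**6. Is the ordinary interval misleading in itself?** I used the exact 95% interval with n = 15 if the trial stops and n = 43 otherwise, and enumerated its coverage over true rates from 0.45 to 0.90. Coverage runs from 0.943 to 0.985. It is a valid descriptive interval under this design.

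**The case for a change.** The strongest case for changing the plan is that pre-specification has value only before the count is known, and that it would take only a few lines. The omission is real and appears in both places, so it is not a fault of extraction. At 30 responses the unnamed method decides whether 55% lies inside the interval. Results of 29 or 30 make up nearly a third of rejections if the true rate is 70%. Moving to an ordinary 90% interval would not reliably cure the mismatch: at 29/43 the exact 90% lower limit is 53.9%, and Wilson's is 54.96%. A two-stage 90% interval with its matching p-value would agree with the rule throughout.

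The arithmetic in that argument stands. The conclusion does not follow from it, because the plan does not use an interval or a p-value to judge success. The choice of method at 30 affects how the result looks, not the decision. The 0.067 comes from a single-stage test that the plan never proposes and that ignores its design. A second interval at another level beside the 95% one is a matter of presentation on which statisticians differ, and the report would then have to explain two intervals.

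**Conclusion.** No change is needed. Success on the primary endpoint is fixed by an explicit count rule whose error rates reproduce, and the analysis population is stated. Following the plan as written gives a sound decision. A two-sided 95% interval beside a one-sided 5% test answers a different question, so a rejected 55% lying inside the interval is not a contradiction.

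The visible mismatch is confined to 29 responses, and to 30 with some methods. At a true rate of 75% these two counts together have probability 0.119. The sample size, type I error, power and stopping rule are untouched.

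An analyst would ordinarily report the exact interval, name it, and note that the count rule decides. If a p-value were wanted, the one consistent with the design is the two-stage value (0.0496 at 29/43). This is a gap in reporting detail that competent practice fills. The conclusion assumes 43 treated patients and the usual two-sided reading of the 95% interval.
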